1. SYNOPSIS

A supraglottic airway device (SAD) is used in the airway management of patients undergoing general anaesthesia. It has two major components, a 'mask' which forms a seal over the glottis with or without the use of an inflatable cuff, and an 'airway tube' which transmits gases during ventilation from the mask to the anaesthetic breathing system. In the years since the introduction of the SADs numerous new devices have been developed. Initially these shared similar characteristics with the first devices and have been named '1st generation' devices. The use of these devices carries a low but recognised risk of complications including aspiration of gastric contents, inadequate laryngeal seal, post-operative sore throat and difficulties with device insertion. In an attempt to address these issues manufacturers have developed '2nd generation' SADs, which are designed to reduce the risk of aspiration and may claim features such as easier insertion, reduced trauma on insertion, superior seal pressures, and integral bite blocks. The LMA® Protector™ is a CE marked new single use SAD developed by Teleflex inc. It is a 2nd generation device which has a number of additional features compared to previous designs, incorporated to improve the safety of the device. We propose a national multi-centre prospective controlled clinical evaluation cohort study, to study the performance of the device and determine its likely place in clinical practice in the UK.

Study Title	Observational study of LMA Protector	
Internal ref. no. / short title	ADEPT 1	
Study Design	Prospective, multi-centre cohort study	
Study Participants	Adult patients undergoing general anaesthesia with a SAD.	
Planned Sample Size	1100 - 2000	
Planned Study Period	2 years	
	Objectives	Outcome Measures
Primary	To assess overall performance of the LMA Protector	1)First go insertion success rate, 2)First go successful ventilation rate, 3)Percentage of complication free insertions
Secondary	To assess: 1) Time taken to achieve airway 2) Number of attempts to achieve patent airway 3) Complications during airway insertion 4) Complications during anaesthesia attributed to the airway 5) Complications during device removal 6) Complications after anaesthesia attributed to the airway 7) Quality of ventilation	1) Time to first square capnography waveform 2) Lowest oxygen saturation level 3) Monitor numbers of interventions needed to ensure airway patency 4) Monitor pre-defined complications occurrence during insertion of device, during anaesthesia, and on device removal 5) The quality of ventilation will depend on whether there was: a) adequate chest

		movement, b) tidal volume > 7ml/kg, c) stable SpO ₂ , and d) square capnography trace
--	--	--

2. ABBREVIATIONS

ASA	American Society of Anesthesiologists
ADE	Adverse Device Effect
CI	Chief Investigator
CRF	Case Report Form
GCP	Good Clinical Practice
HRA	Health Research Authority
ICF	Informed Consent Form
LMA	Laryngeal Mask Airway
NHS	National Health Service
NRES	National Research Ethics Service
PACU	Post Anaesthesia Care Unit
PI	Principal Investigator
PIL	Participant/ Patient Information Leaflet
R&D	NHS Trust R&D Department
REC	Research Ethics Committee
SADE	Serious Adverse Device Effect
SOP	Standard Operating Procedure
SAD	Supraglottic Airway Device
TSG	Oxford University Hospitals NHS Foundation Trust/University of Oxford Trials Safety Group.
TV	Tidal Volume
UADE	Unanticipated Adverse Device Effect

3. BACKGROUND AND RATIONALE

Background

A supraglottic airway device (SAD) is used in the airway management of patients undergoing general anaesthesia. It has two major components, a 'mask' which forms a seal over the glottis with or without the use of an inflatable cuff, and an 'airway tube' which transmits gases during ventilation from the mask to the anaesthetic breathing system (1). After the patient is anaesthetised, the device is advanced into the mouth over the tongue into the pharynx, resting in the hypopharynx and covering the supraglottic structures. This enables relative isolation of the trachea from other structures such as the oesophagus. Although the use of

SADs is primarily to enable ventilation during general anaesthesia where endotracheal intubation is deemed unnecessary or inappropriate, they also have an important role in the management of the difficult airway either as a rescue device or as a channel to intubate the trachea via fibre optic intubation (2).

The original SAD, the laryngeal mask airway (LMA), was developed in the UK by Archie Brain and entered widespread use in 1989. Now named the LMA classic (cLMA) it was quickly adopted by the profession and revolutionised anaesthetic practice around the world. In 2010 the Royal College of Anaesthetists (RCOA) carried out the 4th National Audit Project, which analysed major complications of airway management in the UK. At this time, a SAD was in use in more than 50% of all general anaesthetics, the majority using either the cLMA or similar design (3,4).

In the years since the introduction of the cLMA numerous new SADs have been developed. Initially these shared similar characteristics with the cLMA and have been named '1st generation' devices. The use of these devices carries a low but recognised risk of complications including aspiration of gastric contents, inadequate laryngeal seal, post-operative sore throat and difficulties with device insertion (3). In an attempt to address these issues manufacturers have developed '2nd generation' SADs, which are designed to reduce the risk of aspiration and may claim features such as easier insertion, reduced trauma on insertion, superior seal pressures, and integral bite blocks (5,6). These improvements have led to true advancement in the field (7-10) and have led to calls from experts for 2nd generation device use to become a standard of care (11).

In 2011 the Difficult Airway Society (DAS), in response to concerns from the anaesthetic community that devices used in airway management were being introduced into clinical practice with minimal trial based evidence of their benefit, formed the ADEPT (Airway Device Evaluation Project Team) working group. The group made a number of recommendations on the evaluation of airway equipment prior to purchase, published in *Anaesthesia* in 2011 (12). These were subsequently adopted by DAS as guidance to its members involved in the procurement of airway equipment. The ADEPT guidance identifies that, although such devices may be sold under the Medical Devices Directive with little evidence of efficacy and safety, they should not be bought and used unless there is a minimum standard of evidence available proving such. The minimum acceptable level of evidence according to ADEPT guidance is 3b, i.e. a single case-control or historical case-control study, with more robust evidence preferred if feasible and practical. The guidance is clear that it does not consider RCT (1b) or systematic review (1a) to be necessary for airway device evaluation where more pragmatic and less resource intensive study designs may be adequate (12).

Rationale

The LMA® Protector™ is a new single use SAD developed by Teleflex inc. It is a 2nd generation device which has a number of additional features compared to previous designs, incorporated to improve the safety of the device (13). These features are:

- Allows access to and functional separation of respiratory and digestive tracts
- Two drainage channels enabling either direct suction at the upper oesophageal sphincter or the passage of a gastric tube
- Integrated bite block

- A fixation system preventing proximal displacement
- An elongated cuff enhancing the seal at the distal end of the mask at the upper oesophageal sphincter, designed to potentially reduce risk of aspiration
- An integrated cuff pressure indicator enabling continuous monitoring of cuff pressure and optimisation (Cuff Pilot™ Technology)
- Enables passage of tracheal tubes up size 7.5mm internal diameter

The device is an evolution on the design of previous 2nd generation SADs developed by Intavent Orthofix and now owned by Teleflex which are in everyday use around the world - LMA® ProSeal™, the LMA® Supreme™, and the Guardian CPV™ airways, all with good evidence of safety and efficacy (7-10).

The LMA® Protector™ is CE marked, produced in a number of sizes, and has been marketed for clinical use since mid-2016, without any design changes until now, and there is as yet only limited trial data on its use beyond pilot studies (14). Given the enhanced design of the LMA® Protector™ there are clear potential advantages to its use, and trial data is required to determine its safety and efficacy. In order to fulfil the ADEPT guidance minimum standard of evidence the device must be further evaluated before it may be safely recommended for purchase by hospital trusts in the UK. We propose a national multi-centre prospective controlled clinical evaluation cohort study, as sufficient to delineate the performance of the device and determine its likely place in clinical practice in the UK (or similar) rather than presupposing we will "recommend it". The LMA® Protector™ is not used in standard care in any of the hospital trusts involved in the study.

Study outline and research questions

We will conduct a prospective multi-centre cohort study to evaluate the performance of the device. The main research questions pertain to the device performance, focusing on quality of the airway, ease of insertion, quality of ventilation, and incidence of complications.

Participants

All patients aged above 18, ASA grade 1 to 3, presenting for elective surgical procedures and requiring and suitable for a supraglottic airway device will be invited to take part in the study. Exclusion criteria are: a) patient refusal, b) below 18 years of age, c) requiring intubation, d) risk factors for aspiration, e) ASA 4 and above, f) mouth opening of less than 2.5cm and deemed to require awake intubation.

Potential risks

The potential risks and burdens are the same compared to using other airway devices during anaesthesia. We will minimise them by ensuring adequate training in the use of the device is used, by recruiting investigators who are anaesthetists with experience of using similar airway devices more than 200 times.

4. OBJECTIVES AND OUTCOME MEASURES

Objectives	Outcome Measures	Timepoint(s) of evaluation of this outcome

		measure (if applicable)
Primary Objective To assess the performance of the LMA Protector	1) First go insertion success rate, 2) First go successful ventilation rate, 3) Percentage of complication free insertions	At time of anaesthesia
Secondary Objectives To assess: 1) Time taken to achieve airway 2) Number of attempts to achieve patent airway 3) Complications during airway insertion 4) Complications during anaesthesia attributed to the airway 5) Complications during device removal 6) Complications after anaesthesia attributed to the airway 7) Quality of ventilation	1) Time to first square capnography waveform 2) Lowest oxygen saturation level 3) Monitor numbers of interventions needed to ensure airway patency 4) Monitor pre-defined complications occurrence during insertion of device, during anaesthesia, and on device removal 5) The quality of ventilation will depend on whether there was: a) adequate chest movement, b) tidal volume $> 7\text{ml/kg}$, c) stable SpO ₂ , and d) square capnography trace	At time of anaesthesia and post-operatively

5. STUDY DESIGN

This is a prospective, multi-centred cohort observational study, where all suitable participants will have the LMA Protector used. The centres involved will be: Oxford University Hospitals NHS Foundation Trust, Northampton General Hospital, Royal Berkshire Hospital, Royal United Hospital, and University Hospital of Wales. The participants will be involved in the study for maximum 48 hours starting from approach for consent on the morning of surgery, while they are in the pre-operative area, until the second interview (either in person if participant is an inpatient, or via telephone if participant had been discharged). Data will be collected while the anaesthetic is being conducted apart from the information regarding the complications of the device removal and postoperatively. The order of events will be: a) consent, b) general anaesthetic as per standard care but using LMA protector, c) brief interview by clinician following operation in hospital at first available opportunity, d) another interview 24 to 48 hours later with the same questions either in hospital or at home by telephone.

Data that will be collected will be: a) investigator name, b) number of previous insertions of the device by the investigator, c) patient age, d) patient gender, e) weight, f) height, g) ASA class, h) operation, i) anaesthetic drugs and dosages, j) anaesthetic technique, k) mode of ventilation, l) if further muscle relaxant used. Moreover, we will collect:

- 1) Airway assessment including Malampatti classification
- 2) The number of attempts at the insertion will be recorded

- 3) Volume of air in cuff to achieve intracuff pressure of 60cmH₂O
- 4) Airway leak pressure
- 5) The ease of insertion
- 6) The lowest oxygen saturation recording
- 7) The quality of ventilation
- 8) The quality of the airway during maintenance
- 9) The ease of hands free anaesthesia
- 10) The overall usefulness of the device in the patient
- 11) The overall performance of the device
- 12) The time to first square capnography trace
- 13) Positive or negative bubble test
- 14) Airway manipulations to establish airway
- 15) Complications on insertion, during use, and on removal of the device
- 16) Post-operative oropharyngeal sequelae

The data will be collected from the anaesthetic record. Data c, d, e, f will be collected from the electronic notes.

All data will be recorded in the CRF/data collection form.

6. PARTICIPANT IDENTIFICATION

6.1. Study Participants

Inclusion Criteria

- Adult participants who are having a general anaesthetic.
- Participant is willing and able to give informed consent for participation in the study.
- Male or Female, aged 18 years or above.
- ASA 1 – 3 category patients
- Elective operations
- Urgent operations
- Patients suitable for an SAD based on patient and operation factors.

6.2. Exclusion Criteria

The participant may not enter the study if ANY of the following apply:

- Refusal of consent
- Age less than 18 years
- Require intubation for the operation
- Risk of regurgitation
- ASA 4 and above
- Mouth opening less than 2.5cm
- Require awake intubation

7. STUDY PROCEDURES

7.1. Recruitment

Potential participants will be identified on the morning of surgery during the preoperative anaesthetic visit. The investigator will be a member of the direct care team, i.e. the anaesthetist for the case. The investigator will examine whether the potential participant fulfils any of the inclusion criteria and none of the exclusion criteria apply to them. The

participant information leaflet will be given to the patient, the investigator will answer any questions the patient might have, and at least one hour will be given to the patient, which the study team feels this is an acceptable amount of time to ensure they have not been rushed into taking a decision. They will be asked to sign the consent form, of which the participant will keep a copy, another copy will be placed in the study file, and the original will be placed in the patient's note.

7.2. Screening and Eligibility Assessment

On the morning of surgery, the investigator will examine their operating list and decide if the operations are suitable for the LMA Protector. The investigator will be a member of the direct care team, i.e. the anaesthetist for the case.

If the patients do not meet any exclusion criteria then they will be asked whether they wanted to participate in the study, the PIL will be given to them and they will be given at least one hour to make up their mind. The investigator will then approach the patient again, answer any remaining questions and obtain informed consent.

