Once deep plane of anaesthesia is confirmed, with the absence of movement to jaw thrust stimulation the SAD (LMA protector) will be inserted. The size of the device will be based on the manufacturer's recommendations for the body weight. The breathing system will be connected to the device. Ventilation of the lungs will be then confirmed by observing adequate bilateral chest inflation and square end-tidal capnogram wave with positive pressure ventilation. Adequate ventilation will be recorded if three tests are passed: 1) adequate chest movement, 2) an expired tidal volume of at least 7 ml/kg and 3) stable oxygenation. Time would continue until LMA® ProtectorTM inserted successfully. If it is not possible to insert the device or ventilate through it, two more attempts at placement of the device will be allowed. If placement has failed after two further attempts, the study will be abandoned and the other device will be used. If this fails on first attempt a different LMA or tracheal tube will be used as appropriate.

Maintenance of anaesthesia and recovery

At the end of operation, anaesthetic agents will be discontinued while the device is left in place. The device will be removed after the patient has regained consciousness, and has responded to verbal command to open the mouth. Any complications that occur during the use of the device will be recorded.

Postoperative assessment

Postoperatively in recovery or on the ward, we will visit each patient and determine whether the following airway complications are present after surgery: sore throat (constant pain, independent of swallowing), dysphagia (difficulty in, or pain provoked by, swallowing), sore jaw, dysphonia (difficulty in, or pain on, speaking), numbness of the tongue or the oropharynx, ear pain, neck or mouth ache, hearing changes. Each complication will be graded as none, mild, moderate or severe. The same questions will be asked 24-48 hours later.

The main interventions refer to the insertion of the airway device into the patient to obtain a airway and allow the conduct of the anaesthetic and therefore the surgery. However, if there are problems with the device and the airway obtained is suboptimal then the below interventions are allowed (which will be noted in the data collection form):

- 1) Neck extension – move patient's neck upward
- 2) Neck flexion – move patient's neck downward
- 3) Chin lift - manoeuvre to open the airway
- 4) Jaw thrust – manoeuvre to open the airway

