11.2. Data Recording and Record Keeping

Data will be collected prospectively on data collection sheets completed by the anaesthetist / investigator during anaesthesia. Each site will manage their own data set and the data will be pooled at the end of the recruitment phase across all sites. Data will be sent from sites to the lead study team only at the end of the data collection.

Consent form and initial data collection forms will be filed in the master folder and kept locked in the dedicated research locker in the department.

Each site will assign a study ID for each participant and a record of these IDs will be kept in the site file. Only anonymised data will be sent from each trust to the main study team. No personal data will be sent to the coordinating centre.

Management of data at sites

At each participating site participants will be assigned a trial ID at the moment of enrolment. The log of trial IDs and patient data will be kept in the site file in a locked cupboard in the anaesthetic department in each site. It will be separate to the CRF. The PI at each site will have access to this log.

The trial ID will be noted on the CRF and the consent form.

Data will be recorded by hand on the CRF by the investigator and later will be transcribed on a study database / excel spreadsheet kept on the Trust servers. The CRF will be identifiable by study ID only.

The hard copies of the consent forms and CRF will be kept locally, but separately, in the anaesthetic departments in secure locked filing cabinets.

Electronic data will be kept on a password protected database/excel spreadsheet stored on NHS servers on the hospital intranet of each site (this means it is backed up).

Telephone numbers will be accessed from hospital records with the consent of the participant. If the investigator chooses to record the telephone number of patient, this will be recorded on a separate electronic file, not on the enrolment log, and the file will be destroyed within three months of the study ending. The PI on each site will have access to the research files. Personal data be kept for 3 months and study data be kept for 5 years.

The only data that will be shared with the lead study team will be the data spreadsheet that will only have study IDs and no identifiable data. It will be sent electronically and the password will be sent separately to the spreadsheet.

Data from the research sites will be shared with the lead site only by using secure NHS email accounts.

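### Section 7.2 screens on suitability for the LMA Protector, sections 3, 6.1 and 7.1 on general SAD criteria, and no one counts the eligible patients passed over; the failure rate may be biased low

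*Combined protocol and SAP*

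**What the plan says.** The combined protocol and SAP describes who is approached in several places.

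- **Section 3 (Participants):** all adults of the stated ASA grades "requiring and suitable for a supraglottic airway device will be invited to take part in the study".
- **Section 6.1:** the relevant inclusion criterion is "Patients suitable for an SAD based on patient and operation factors".
- **Section 7.1:** recruitment checks the listed criteria only: "The investigator will examine whether the potential participant fulfils any of the inclusion criteria and none of the exclusion criteria apply to them".
- **Section 7.2:** before the exclusion check and the invitation, "the investigator will examine their operating list and decide if the operations are suitable for the LMA Protector". On who does this: "The investigator will be a member of the direct care team, i.e. the anaesthetist for the case".
- **Section 5:** the design is one "where all suitable participants will have the LMA Protector used", with suitability left undefined.

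On records, section 11.2 says that "participants will be assigned a trial ID at the moment of enrolment". The log it describes therefore begins with enrolled patients. No section asks for consecutive approach, a screening log, or a count of eligible patients who were not invited. Sections 10.1 and 10.3 limit the analysis to single-arm descriptive statistics with binomial confidence limits.

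**The concern.** Taken literally, section 7.2 adds a gate that the eligibility sections do not contain. An operation that suits an SAD in general, but that the anaesthetist thinks less suited to this device, is eligible under sections 3 and 6.1 and yet is never approached under 7.2. No criterion for the extra judgement is given.

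The person at the gate has a part in the outcome. The anaesthetist for the case uses the device, completes the data sheet during the anaesthetic (11.2) and scores its performance (7.5). First-go insertion and first-go ventilation are primary outcomes (section 4).

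With no control arm, the failure proportion is the main result, and section 3 wants it to show where the device belongs in UK practice. If the patients passed over would have failed more often than those enrolled, the proportion is too low for the population named in section 6.1. Nothing in the planned data would show this, and the missing count cannot be reconstructed after recruitment.

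**Working it through.** **1. What the plan's own limits cover.** Section 10.3 gives upper 95% limits of 6.54% (n = 1000) and 6.05% (n = 2000) for a 5% failure rate. The two-sided exact (Clopper-Pearson) interval reproduces both: 50/1000 gives 6.539% and 100/2000 gives 6.048%. At n = 1100, 55 failures give 3.79% to 6.46%. These limits express random error only. More patients narrow them but do nothing about who was selected.

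**2. A simple model of selection.** Inputs:

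- p = 5%, the failure rate of clinical importance in section 10.3, taken here as the true rate among all SAD-suitable patients.
- n = 1100, the interim size in section 10.2.
- h, the share of harder cases; r, their failure risk relative to the other cases; s, the fraction of them left out. **The documents give none of these. They are assumptions**, varied over h = 5% to 20%, r = 1 to 5 and s = 50% to 100%.

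Formulas:

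- Failure rate in the other cases: e = p / (1 − h + h·r)
- Failure rate in the harder cases: r·e
- Observed rate: [(1 − h)·e + h·(1 − s)·r·e] / (1 − h·s)

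**3. Worked case, h = 10%, r = 3.** e = 5% / (0.9 + 0.3) = 4.17%, and the harder cases fail at 3 × 4.17% = 12.5%.

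- Half left out: (0.9 × 4.17% + 0.05 × 12.5%) / 0.95 = 4.61%.
- All left out: the observed rate is e = 4.17%.

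**4. Range.** The intervals are exact, with the failure count rounded to a whole number out of 1100.

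| h | r | s | Observed rate | 95% CI at n = 1100 |
|---|---|---|---|---|
| any | 1 | any | 5.00% | 3.79–6.46% |
| 5% | 2 | 50% | 4.88% | 3.71–6.36% |
| 10% | 3 | 50% | 4.61% | 3.47–6.05% |
| 10% | 3 | 100% | 4.17% | 3.08–5.54% |
| 20% | 3 | 100% | 3.57% | 2.53–4.82% |
| 20% | 5 | 100% | 2.78% | 1.92–3.98% |

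The shift runs from nothing to 5.00 − 2.78 = 2.22 percentage points. In the last two rows the whole interval lies below the true 5%. The first row matters as much: if the omitted patients fail no more often, selection leaves the rate unchanged.

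**The case against.** The best case on the other side is that section 7.2 is loosely worded and adds no second filter. Section 8.1 treats the two terms as one ("the SAD (LMA protector) will be inserted"), the device is itself an SAD, and no device-specific eligibility limit appears anywhere. Section 7.1 is also imprecise: read literally, meeting any one inclusion criterion would do. On this view 7.2 only sorts the list into SAD and non-SAD cases, after which patients meeting no exclusion are asked to take part. This is plausible, and it rules out calling the passages a proven conflict of rules. It does not remove the need to reconcile them, since sites will work from 7.2 as written.

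A reader might infer that anaesthetists will choose by expected success, so that the failure rate is biased low. The documents do not support that. Section 7.2 speaks of operations and does not mention difficult airways or predicted success. Section 6.1 already admits operation factors. Section 6.2 removes several harder groups by rule, which limits what is left to omit. A low bias also requires that the omitted patients fail more often, which no section states.

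A reader might also build a striking figure from the 2.5% rule in section 10.2, which at n = 1100 allows at most 17 failures (upper limit 2.46%). Suppose 90% of patients fail at 1.5% and 10% at 8%, a true rate of 2.15%. The chance of meeting the rule is then 10% with everyone enrolled, 28% with half the harder cases left out (rate 1.84%) and 61% with all left out (rate 1.5%). The arithmetic is right, but the inputs are chosen and put the true rate close to the threshold. With the 5% worked case (observed 4.17%), the chance of 17 or fewer failures stays below 0.0001%. The jump is one scenario and not a finding.

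One further objection stands. Section 6.1 leaves discretion to the same anaesthetist, so aligning the words alone would not remove the risk.

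**Conclusion.** The point holds as a risk. The screening step in 7.2 is worded differently from sections 3, 6.1 and 7.1, the person applying it also inserts and scores the device, and no count of eligible but unapproached patients is kept. The failure rate may therefore be biased low, on the condition that those passed over fail more often.

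The documents cannot give the size. At a true rate of 5%, under the assumed ranges, the observed rate lies anywhere from 5.00% (no effect) down to 2.78%. The central illustration, 10% harder cases at three times the risk and all omitted, gives 4.2%. These values show scale and are not estimates.

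This is a cheap improvement to make before recruitment and does not undermine the design. Even if selection proves harmless, the tally is what would let a reader judge how widely the failure rate applies.

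**What to change.** 1. Reconcile section 7.2 with sections 3, 6.1 and 7.1 so that one eligibility definition governs screening. Which clinical judgement of suitability applies is for the investigators to settle; the sections need to agree. Sections 3 and 6.1 also differ on urgent operations and should be aligned in the same edit.
2. State that eligible patients on a study list are invited in order.
3. Keep an anonymised tally for each list: eligible, invited, consented, device used, and the reason if not. Include any case judged unsuitable for this particular device, so that such judgements are recorded and not barred.
4. Report the enrolled share of eligible patients by site, beside the primary failure rates.

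The cost is a few sentences in the protocol and a short tally sheet per list, a minor paperwork burden on the anaesthetists. The tally holds counts and reasons only, so it fits the rule in section 11.2 that only anonymised data leave a site.
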